9.1.6. End of Blinded Treatment Visit; Return to the Clinic

At the time a patient permanently discontinues blinded study treatment or has PD prior to unblinding of all patients at the end of Phase 3 (ie, when the required number of PFS events for the primary PFS analysis are observed), a visit should be scheduled as soon as possible (within 14 days), at which time all of the assessments listed for the End of Blinded Treatment (EoBT) Visit will be performed. Study procedures will be performed ≤ 14 days after the last dose of study treatment, as specified in Table 1. An EoBT CRF page will be completed, giving the date and reason for stopping the study treatment. Patients lost to follow-up should be recorded as such on the appropriate eCRF.

For patients proceeding to open-label selinexor, the EoBT Visit will serve as the baseline for the open-label treatment phase. After the unblinding following the PFS analyses, patients in the selinexor arm who are continuing on selinexor but as open-label treatment must complete their EoBT Visit before their next scheduled selinexor dose.

- Informed consent for open-label selinexor (only for patients proceeding to open-label selinexor) and Assent Form for adolescent patients (permitted only in countries in

which adolescents have been approved by the national/local regulatory/ethical authority)

- Physical examination and vital signs (blood pressure, pulse, and body temperature) (Section 10.6.1.1)
- Weight, height, and BSA (Section 10.6.1.2)
- ECOG performance status assessment (Section 10.6.1.3)
- 12-lead ECG (Section 10.6.1.4)
- Urinalysis (Section 10.6.2.1)
- Hematology (Section 10.6.2.1)
- Complete serum chemistry (Section 10.6.2.1)
- Coagulation tests (Section 10.6.2.1)
- Serum hCG pregnancy test (females of childbearing potential only). Females of childbearing potential who are proceeding to open-label selinexor must have a negative serum hCG pregnancy test at the EoBT Visit (or within 3 days before the first dose of open-label selinexor). (Section 10.6.2.2)
- Tumor biopsy for patients who were in the placebo arm and are crossing over to open-label selinexor only. If the patient has archival material (ie, of DDLS tissue) collected at Screening, Cycle 1 Day 22, or Cycle 2 Day 1 within 12 months prior to the first dose of open-label selinexor, that sample may substitute for the biopsy. Patients in the selinexor arm who continue on selinexor but as open-label treatment are not required to have an additional tumor biopsy at the EoBT Visit. See Section 10.11.3.
- Imaging to evaluate site of disease and distant sites (abdomen, pelvis, chest)
 - Phases 2 and 3: CT (preferred) or MRI scan for tumor measurement (if \geq 4 weeks since last prior scan AND required to document disease or clinical progression) for assessment of liposarcoma. Patients in the placebo arm who have clinical progression must have subsequent radiographic progression determined by the central reader in order to receive open-label selinexor.
- Assessment of progression/extent of liposarcoma by RECIST v. 1.1 (2) if tumor (CT/MRI) scan is performed.
- Treatment assignment query of patients and Investigators (if not performed at a previous visit; query after PD but prior to unblinding) (Section 10.7.2).
- QoL questionnaires (EORTC QLQ-C30 and EuroQoL EQ-5D-5L) (Section 10.7.1)
- AEs/SAEs
- Concomitant medications
- Information on any antineoplastic therapies used since discontinuation of blinded study treatment

9.1.7. Safety Follow-up Phone Call (30 Days [+7 days] after last dose of study treatment)

Only for patients NOT proceeding to open-label selinexor.

At a minimum, all patients who discontinue study treatment, including those who refuse to return for an EoBT Visit, will be contacted for safety evaluations during the 30 days (+7 days) following the last dose of study treatment. Every effort should be made to contact the patient (or the patient's family) by telephone or by sending appropriate correspondence (eg, certified letter or email).

During this patient contact the most important information to be obtained includes the following:

- Overall medical condition of the patient and status of their liposarcoma
- AEs, including follow-up on any AEs that were not resolved at the EoBT Visit
- Collection of information (including treatment type, response, and time of response for assessment of CCI) on any antineoplastic therapies used after discontinuation of blinded study treatment. For patients who progress on post-study treatment antineoplastic therapy, the Investigator should enter the date of progression from the medical record in the eCRF if that information is available to the Investigator.

9.1.8. Survival Follow-Up

Only for patients NOT proceeding to open-label selinexor.

After discontinuation of blinded study treatment, a call will be made to the patient (or the patient's family) every 3 months to inquire about the patient's liposarcoma status, well-being, and information on any antineoplastic therapies used since discontinuation of study treatment (for assessment of CCI). If the patient has died, the patient's date of death will be collected, together with the reason for death, if possible.

Patients lost to follow up should be recorded as such on the eCRF-. For patients who are lost to follow-up, the Investigator should show "due diligence" by documenting in the source documents steps taken to contact the patient, eg, dates of telephone calls, registered letters, etc. (see Section 11.2).

9.2. Description of Study Days: Open-label Selinexor

Please note:

- EoBT Visit serves as baseline of Open-Label Selinexor; The EoBT Visit may occur on the day of the patient's first open-label dose (OL-C1 D1 Visit) but must be ≤ 14 days of last blinded dose. OL C1 D1 must occur within 14 days of the EoBT Visit.
- Patients in the selinexor arm who continue selinexor but as open-label treatment must complete the EoBT Visit before their next scheduled selinexor dose to maintain continuity of selinexor dosing from blinded to open-label treatment.
- Physical examination assessments and laboratory assessments done at the EoBT Visit do not need to be repeated at OL C1 D1.

9.2.1. Visits OL1-6 (Cycle 1: Days 1, 8*, 15*, 22, 29*, and 36* [± 1 days]); Return to the Clinic

There are six clinic visits (ie, Days 1, 8*, 15*, 22, 29*, and 36*) during the first six-week cycle (Cycle 1).

Visits (ie, Days 8, 15*, 29*, and 36*) are not required for patients who continue selinexor but as open-label treatment.

The following study assessments will be performed during Cycle 1, as specified in [Table 2](#).

- Physical examination and vital signs (blood pressure, pulse, and body temperature) (Days 8*, 15*, 22, 29*, and 36*) [Section 10.6.1.1](#)
- Weight (Days 8*, 15*, 22, 29*, and 36*) ([Section 10.6.1.2](#))
- Limited serum chemistry (Days 8*, 15*, 22, 29* and 36*) ([Section 10.6.2.1](#))
- Tumor biopsy, only for patients who cross over from blinded placebo to open-label selinexor and have sufficient material available from a biopsy sample obtained during blinded study treatment (pre- or post-dosing) within 12 months prior to the first dose of open-label selinexor (Day 22 only). Note: If the biopsy is not performed on Cycle 1 Day 22, it may be performed on Cycle 2 Day 1 (see [Section 9.2.2](#)). Patients in the selinexor arm who continue on selinexor but as open-label treatment are not required to have an additional tumor biopsy on Cycle 1 Day 22 of open-label treatment. See [Section 10.11.3](#) for biopsy details.
- CCI
- CCI
- Nutritional consultation (should occur on Day 1 before the first dose of open-label selinexor) for patients in the placebo arm who cross over to open-label selinexor. The nutritional consultation is not required at C1 D1 of open-label selinexor treatment for patients in the selinexor arm who continue on selinexor but as open-label treatment. See [Section 10.7.3](#).
- Selinexor: in clinic dosing and dispensing of for home use
- AEs and SAEs (throughout the cycle)
- Concomitant medications (throughout the cycle)

The following OL1 Visit (C1 D1) assessments will be performed only if they were not performed at the EoBT Visit:

- Informed consent for open-label selinexor and Assent Form for adolescent patients (permitted only in countries in which adolescents have been approved by the national/local regulatory/ethical authority) must be signed on or before the OL1 Visit

before any study-specific procedures for treatment with open-label selinexor are conducted at the OL1 Visit (Day 1 only)

- Physical examination and vital signs (blood pressure, pulse, and body temperature) (Day 1) Section [10.6.1.1](#))
- Weight (Day 1) (Section [10.6.1.2](#))
- ECOG performance status assessment (Day 1 only) (Section [10.6.1.3](#))
- 12-lead ECG (Day 1 only) (Section [10.6.1.4](#))
- Urinalysis (Day 1 only) (Section [10.6.2.1](#))
- Hematology (Day 1 only) (Section [10.6.2.1](#))
- Complete serum chemistry (Day 1 only) (Section [10.6.2.1](#))
- Coagulation tests (Day 1 only) (Section [10.6.2.1](#))
- QoL questionnaires (EORTC QLQ-C30 and EuroQoL EQ-5D-5L); Day 1 only, predose) (Section [10.7.1](#))

9.2.1.1. Phone Call with Patient: Cycle 1 Day 3 Only (+ 1 day)

A phone call will be made to the patient to evaluate supportive care medications, concomitant medications, and AEs/SAEs, and to adjust supportive care as appropriate.

9.2.2. Visits OL7-9 (Cycle 2: Days 1, 15, and 29* [± 2 days]); Return to the Clinic

There are three clinic visits (Days 1, 15, and 29*) for Cycle 2.

Visit (ie, Day 29) is not required for patients who continue selinexor but as open-label treatment.

The following study assessments will be performed during Cycle 2, as specified in [Table 2](#).

- Physical examination and vital signs (blood pressure, pulse, and body temperature) (Days 1, 15, and 29*) (Section [10.6.1.1](#))
- Weight (Days 1, 15, and 29*) (Section [10.6.1.2](#))
- Height and BSA (Day 1 only) (Section [10.6.1.2](#))
- ECOG performance status assessment (Day 1 only) (Section [10.6.1.3](#))
- Urinalysis (Day 1 only) (Section [10.6.2.1](#))
- Hematology (Day 1 only) (Section [10.6.2.1](#))
- Complete serum chemistry (Day 1 only) (Section [10.6.2.1](#))
- Limited serum chemistry (Days 15 and 29 only) (Section [10.6.2.1](#))
- Coagulation tests (Day 1 only) (Section [10.6.2.1](#))
- Female patients of childbearing potential only: pregnancy test (serum hCG or high sensitivity urine) prior to dosing on Day 1 only. A positive urine pregnancy test will be confirmed by a serum pregnancy test. (Section [10.6.2.2](#))
- Tumor biopsy only for patients who cross over from blinded placebo to open-label selinexor and have sufficient material available from a biopsy sample obtained during blinded study treatment (pre- or post-dosing) within 12 months prior to the first dose

of open-label selinexor (Day 1 only and only if not taken at Cycle 1 Day 22, see Section 9.2.1). Patients in the selinexor arm who continue on selinexor but as open-label treatment are not required to have an additional tumor biopsy on Cycle 2 Day 1 of open-label treatment. See Section 10.11.3 for biopsy details.

- Imaging to evaluate site of disease and distant sites (abdomen, pelvis, chest)
 - CT (preferred) or MRI scan for tumor measurement approximately 6 weeks post-first dose (ie, Day 1 of Cycle 2) to evaluate site of disease and distant sites (abdomen, pelvis, chest)
- Assessment of progression/extent of liposarcoma by RECIST v. 1.1 (2) approximately 6 weeks after the first dose of open-label selinexor (ie, Day 1 of Cycle 2), based on 6-week tumor scan.
- QoL questionnaires (EORTC QLQ-C30 and EuroQoL EQ-5D-5L) (Day 1 only, predose) (Section 10.7.1)
- Selinexor: in clinic dosing and dispensing of for home use (Days 1, 15, and 29)
- AEs and SAEs (throughout the cycle)
- Concomitant medications (throughout the cycle)

9.2.2.1. Phone Calls with Patient: Cycle 2 Days 10, 24, and 38 (+ 1 day)

A phone call will be made to the patient to evaluate supportive care medications, concomitant medications, and AEs/SAEs, and to adjust supportive care as appropriate.

9.2.3. Visits OL ≥ 10 (Cycles ≥ 3: Days 1 and 22 [± 2 days]); Return to the Clinic

Patients enrolled in this study may continue from cycle to cycle without interruption.

The following study assessments will be performed for Cycles ≥ 3 , as specified in Table 2:

- Physical examination and vital signs (blood pressure, pulse, and body temperature) (Days 1 and 22) (Section 10.6.1.1)
- Weight (Days 1 and 22) (Section 10.6.1.2)
- Height and BSA (Day 1 only) (Section 10.6.1.2)
- ECOG performance status assessment (Day 1 only) (Section 10.6.1.3)
- Urinalysis (Day 1 only) (Section 10.6.2.1)
- Hematology (Day 1 only) (Section 10.6.2.1)
- Complete serum chemistry (Day 1 only) (Section 10.6.2.1)
- Limited serum chemistry (Day 22 only) (Section 10.6.2.1)
- Coagulation tests (Day 1 only) (Section 10.6.2.1)
- Female patients of childbearing potential only: pregnancy test (serum hCG or high sensitivity urine) prior to dosing on Day 1 only. A positive urine pregnancy test will be confirmed by a serum pregnancy test. (Section 10.6.2.2)
- Imaging to evaluate site of disease and distant sites (abdomen, pelvis, chest)
 - CT (preferred) or MRI scan for tumor measurement approximately 12 weeks after start of open-label selinexor (ie, Day 1 of Cycle 3), and approximately

every 12 weeks thereafter (ie, Day 1 of odd-numbered Cycles ≥ 5) to evaluate site of disease and distant sites (abdomen, pelvis, chest); the same imaging modality should be maintained throughout the study

- Assessment of progression/extent of liposarcoma by RECIST v. 1.1 (2) when tumor (CT/MRI) scans are performed. Assessments are to be performed approximately 12 weeks after start of open-label selinexor (ie, Day 1 of Cycle 3), and approximately every 12 weeks thereafter (ie, Day 1 of odd-numbered Cycles ≥ 5), based on tumor scans.
- QoL questionnaires (EORTC QLQ-C30 and EuroQoL EQ-5D-5L) (Day 1 only, predose) (Section 10.7.1)
- Selinexor: in clinic dosing and dispensing of for home use (Days 1 and 22)
- AEs and SAEs (throughout the cycles)
- Concomitant medications (throughout the cycles)

9.2.4. End of Treatment Visit (≤ 14 days after last dose of study treatment); Return to the Clinic

At the time a patient permanently discontinues selinexor a visit should be scheduled as soon as possible (within 14 days), at which time all of the assessments listed for the End of Treatment (EoT) Visit will be performed. Study procedures will be performed ≤ 14 days after the last dose of selinexor as specified in Table 2. An EoT CRF page will be completed, giving the date and reason for stopping the selinexor. Patients lost to follow-up should be recorded as such on the appropriate eCRF.

- Physical examination and vital signs (blood pressure, pulse, and body temperature) (Section 10.6.1.1)
- Weight, height, and BSA (Section 10.6.1.2)
- ECOG performance status assessment (Section 10.6.1.3)
- 12-lead ECG (Section 10.6.1.4)
- Urinalysis (Section 10.6.2.1)
- Hematology (Section 10.6.2.1)
- Complete serum chemistry (Section 10.6.2.1)
- Coagulation tests (Section 10.6.2.1)
- Serum hCG pregnancy test (females of childbearing potential only). (Section 10.6.2.2)
- Imaging to evaluate site of disease and distant sites (abdomen, pelvis, chest)
 - CT (preferred) or MRI scan for tumor measurement (if ≥ 4 weeks since last prior scan AND required to document disease or clinical progression) for assessment of liposarcoma.
- Assessment of progression/extent of liposarcoma by RECIST v. 1.1 (2) if tumor (CT/MRI) scan is performed.
- QoL questionnaires (EORTC QLQ-C30 and EuroQoL EQ-5D-5L) (Section 10.7.1)
- AEs and SAEs

- Concomitant medications
- Information on any antineoplastic therapies used since discontinuation of open-label selinexor

9.2.5. OL Safety Follow-up Phone Call (≤ 30 Days [+7 days] after last dose of study treatment)

At a minimum, all patients who discontinue study treatment, including those who refuse to return for an EoT Visit, will be contacted for safety evaluations during the 30 days (+7 days) following the last dose of study treatment. Every effort should be made to contact the patient (or the patient's family) by telephone or by sending appropriate correspondence (eg, certified letter or email).

During this patient contact the most important information to be obtained includes the following:

- Overall medical condition of the patient and status of their liposarcoma
- AEs, including follow-up on any AEs that were not resolved at the EoT Visit
- Collection of information (including treatment type, response, and time of response for assessment of CCI) on any antineoplastic therapies used after discontinuation of open-label selinexor. For patients who progress on post-study treatment antineoplastic therapy, the Investigator should enter the date of progression from the medical record in the eCRF if that information is available to the Investigator.

9.2.6. OL Survival Follow-Up

After discontinuation of treatment with open-label selinexor, a call will be made to the patient (or the patient's family) every 3 months to inquire about the patient's liposarcoma status, well-being, and information on any antineoplastic therapies used since discontinuation of study treatment (for assessment of CCI). If the patient has died, the patient's date of death will be collected, together with the reason for death, if possible.

Patients lost to follow-up should be recorded as such on the eCRF. For patients who are lost to follow-up, the Investigator should show "due diligence" by documenting in the source documents steps taken to contact the patient, eg, dates of telephone calls, registered letters, etc. (see Section 11.2).

9.3. Unscheduled Visits

Unscheduled visits may be conducted at any time during the blinded or open-label portions of the study at the discretion of the Investigator. Additional testing (eg, blood testing or imaging scans) may be performed to ensure patient safety.

If unscheduled imaging scans are performed, they will be evaluated as described in Section 10.5.1.1. If PD is confirmed based on an unscheduled imaging scan, the options for study treatment described in Section 7.2.1 will apply.

10. METHODS OF ASSESSMENT

10.1. Inclusion/Exclusion Criteria

The patient must meet the all of the inclusion criteria (Section 8.3) and none of the exclusion criteria (Section 8.4).

Key patient eligibility (inclusion/exclusion criteria) will be confirmed by the Sponsor for all patients participating in the study prior to randomization (Section 7.6).

See Section 7.7 for randomization details.

10.2. Demographic Data

Patient demographics (including date of birth, sex, race, ethnicity, age at time of consent, and tumor type) will be collected at study entry.

10.3. Medical History

A complete medical history will be obtained from each patient. Medical history will include baseline liposarcoma symptoms as well as a detailed history of prior procedures and prior cancer therapies (ie, chemotherapy, hormonal therapy, immunotherapy, biotherapy, radiotherapy, and surgery) including start and stop dates, best response, PD during or after therapy, as well as discontinuations due to intolerance or toxicity.

A detailed history of disease-specific diagnostic and prognostic testing and test results (such as phenotypic and cytogenetic profiles) will also be collected.

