8.3. Inclusion Criteria

Patients eligible for inclusion in this study must meet all of the following criteria:

1. Written informed consent in accordance with national, local, and institutional guidelines obtained prior to any screening procedures
2. Must be willing and able to comply with the protocol
3. Patients ≥ 12 years of age (patients <18 years of age are permitted only in countries in which adolescents have been approved by the national/local regulatory/ethical authority).
4. Patients with a body surface area (BSA) $\geq 1.2 \text{ m}^2$ as calculated per [Dubois 1916](#) or [Mosteller 1987](#).
5. Documented histologic evidence of DDLS at any time from initial diagnosis to randomization AND current evidence of DDLS requiring treatment (documented evidence of disease progression from the most recent treatment):
 - Documentation of histologic evidence of DDLS requires the following:
 - This information will be provided based on prior diagnostic testing and is required for randomization.
 - Tissue (fresh or archival) will be provided for confirmatory histology at a central laboratory but confirmatory results are not required prior to randomization.
 - If archival tissue > 12 months old, the quality of the sample for confirmatory histology must be confirmed by the site histopathologist prior to randomization.
6. Must have measurable disease according to:
 - The bidimensional WHO Response Criteria ([Miller 1981](#)) (Phase 2 patients only)
 - RECIST v. 1.1 ([Eisenhauer 2009](#)) ([Phase 3 patients only](#))
7. Radiologic evidence of progressive disease (PD) within 6 months prior to randomization. If the patient received other intervening therapy after PD is documented, further PD must

be documented after the completion of the intervening therapy, with the exception of patients who discontinued most recent treatment after no more than 1 dose.

8. Must have received at least 2 but no more than 5 prior systemic therapies for the treatment of liposarcoma.
9. Patients should have recovered from all major surgery, radiation or other interventions ≥ 21 days prior to randomization. Patients must have recovered from any clinically significant therapy-related toxicity to \leq Grade 1 per CTCAE v. 4.03. Minor procedures, such as biopsies, dental work, or placement of a port or intravenous line for infusion, are permitted.

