3.2.4. Disease History

Disease history data will be summarized by treatment arm, as well as overall, and will include the following variables:

- Time since first initial diagnosis to randomization date
- Time since most recent progression to randomization date
- Stage of current liposarcoma diagnosis

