4.2.2. Other Secondary Efficacy Endpoints

4.2.2.1. Time to Progression (TTP)

Time to progression (TTP) is defined as the time from date of randomization until ICR-determined PD per RECIST v.1.1, or death due to disease progression, whichever occurs first. TTP outcome and censoring definitions are similar to the outcome and censoring definitions for PFS in Table 4-1, with the only exception that only death due to disease progression will be considered a TTP event. Death due to reasons other than disease progression will be a new censoring event under situation #5.

TTP on patient's last prior systemic therapy is defined as time since start of last prior systemic therapy to date of disease progression. For patients without a disease progression date, their TTP will be censored on the discontinuation date of last prior systemic therapy.

The comparison of TTP on study treatment to TTP on last prior therapy will be performed using a stratified Cox proportional hazards regression model stratifying on patient IDs to account for correlation within patient. This analysis will be conducted respectively among Ph3-ITT and Ph2-ITT patients randomized to selinexor.

For exploratory purpose, TTP will be summarized among Ph3-ITT patients randomized to placebo arm, Ph3-OL population, Ph2-ITT patients randomized to placebo arm, and Ph2-OL population respectively. For open-label selinexor, TTP is measured as time since the start of open-label treatment until ICR-determined PD per RECIST v.1.1, or death due to disease progression, whichever occurs first. Median TTP time with 95% CIs will be presented using the KM method.

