4.2.2.5. Time to Next Treatment (TTNT)

[figure not shown]
TTNT is defined as time since randomization until the first new antineoplastic therapy or death due to any cause, whichever occurs first. For patients without an event, their follow-up time will be censored at the date of discontinuation from the study, or date of last participating visit (e.g., a telephone contact with patient status being alive) on or before database cut-off date, whichever occurs first.

TTNT on patient's last prior systemic therapy is defined as time since start of last prior systemic therapy to start of blinded study treatment or death due to any cause, whichever occurs first. For patients who were randomized but never received study treatment, and did not die before discontinuation from study, their follow-up time will be censored at the date of discontinuation from the study, or date of last participating visit (e.g., a telephone contact with patient status being alive) on or before database cut-off date, whichever occurs first.

[figure not shown]
The analysis comparing TTNT on study treatment vs. on last prior systemic therapy will be conducted among patients in the Ph3-ITT population randomized to selinexor and placebo arms separately. To account for within-person correlation, a stratified Cox proportional hazards model analysis will be conducted stratifying on patient IDs. KM median TTNT times with 95% CIs, and KM curves will be provided.

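### SAP 4.2.2.1 censors an undated prior progression that the entry criteria make a known event; where such dates are missing, the within-patient TTP hazard ratio shifts against selinexor

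*Protocol*

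**What the plan says.** A within-patient comparison of TTP on study with TTP on the preceding line is a secondary objective in both phases (Protocol 6.1.2 and 6.2.2; SAP 1.2). SAP 4.2.2.1 defines the comparator: "TTP on patient's last prior systemic therapy is defined as time since start of last prior systemic therapy to date of disease progression". The fallback follows: "For patients without a disease progression date, their TTP will be censored on the discontinuation date of last prior systemic therapy". The two times are compared in a Cox model stratified on patient ID, among patients randomized to selinexor.

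For entry, Protocol 8.3 criterion 5 asks for "documented evidence of disease progression from the most recent treatment". Criterion 7 asks for "Radiologic evidence of progressive disease (PD) within 6 months prior to randomization". If another therapy followed that progression, criterion 7 wants progression again after it, "with the exception of patients who discontinued most recent treatment after no more than 1 dose". Criterion 5 carries no such exception.

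Protocol 10.3 describes the prior-therapy history as "including start and stop dates, best response, PD during or after therapy, as well as discontinuations due to intolerance or toxicity". SAP 3.2.4 lists, among the disease-history summaries, "Time since most recent progression to randomization date". In SAP 4.2.2.5, time to next treatment (TTNT) on the last prior therapy "is defined as time since start of last prior systemic therapy to start of blinded study treatment" or death.

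**The concern.** Under criteria 5 and 7, every patient outside the one-dose exception has progressed after the last prior therapy. What may be unknown is the date, not the event. Protocol 10.3 attaches dates to the start and stop of therapy but not to progression, and the SAP answers a missing date by treating the patient as progression-free at the stop date. This is not neutral, because the censoring falls on one side of a matched pair. At stake is the hazard ratio (study over prior) of a stated secondary comparison, which would move for a reason unrelated to the drug.

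The one-dose exception raises a smaller, linked question. For those patients the qualifying progression may precede the last therapy, so neither the prior TTP nor the prior TTNT clock means what it means for other patients.

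**Working it through.** The plan gives no sample size, effect or power for this comparison, so it has no figure to reproduce.

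**Inputs.** From the documents: the censoring rule and model (SAP 4.2.2.1), and 285 Phase 3 patients randomized 2:1 (SAP 1.1), so about 285 × 2/3 = 190 selinexor pairs. Assumed: the undated share f, and how the stop date relates to the progression date.

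**Step 1, the estimator.** Each stratum holds two times. Let L be the pairs in which study progression is seen first and W the pairs in which prior progression is seen first. Then HR(study/prior) = L/W.

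**Step 2, the effect of the rule.** If the prior time is censored at stop date S, the pair cannot enter W. It enters L if study progression comes before S, and otherwise contributes nothing.

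**Step 3, simplest case.** Let S equal the progression date, with a share f undated at random. L is unchanged and W becomes (1-f)W, so the HR is multiplied by 1/(1-f). With 190 pairs, a true HR of 1 and no study-side censoring, L = W = 95 when all dates are known:

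| f | L | W = 95(1-f) | HR | a true 0.70 reads |
|---|---|---|---|---|
| 0 | 95 | 95 | 1.00 | 0.70 |
| 5% | 95 | 90.25 | 1.05 | 0.70/0.95 = 0.74 |
| 10% | 95 | 85.5 | 1.11 | 0.70/0.90 = 0.78 |
| 20% | 95 | 76 | 1.25 | 0.70/0.80 = 0.88 |

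**Step 4, other patterns.** I simulated 400,000 pairs, assuming a prior median TTP of 4 months, within-patient frailty variance 0.5, study censoring uniform over 1 to 30 months, and a true HR of 1.0 or 0.7. The factor on the HR was:

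- Undated at random, stop date equal to progression date: 1.11 at 10%, 1.33 at 25%, 2.00 at 50%, matching the formula.
- Undated at random, drug stopped at a random point before progression or after a fixed 2- or 4-month course: 1.05 to 1.08 at 10%, 1.16 to 1.25 at 25%, 1.48 to 1.74 at 50%.
- Only progression after the end of a fixed course undated: about 1.00, even with 14% to 73% of patients undated. The stop date is then a common cut that thins L and W in proportion.
- None undated: 1.00. All undated: W = 0 and the HR cannot be estimated.

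**Step 5, one-dose patients.** If no later progression is recorded, prior TTP is censored almost at its start. Study progression will hardly ever come sooner, so the pair is lost without pushing the HR either way. For TTNT, the prior clock runs from the single dose to study start. Criterion 10 sets only a minimum washout (21 days or five half-lives, whichever is shorter), and criterion 7 lets the qualifying progression lie up to 6 months back, so the clock may run from weeks to nearly 6 months. Assume it is uniform over 3 to 26 weeks and study TTNT is exponential with rate λ per week. Study treatment then lasts longer in a share (e^(-3λ) − e^(-26λ))/(23λ) of pairs:

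- Median 3 months (λ = 0.0532): (0.853 − 0.251)/1.223 = 0.49.
- Median 5 months (λ = 0.0319): (0.909 − 0.437)/0.733 = 0.64.

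**The case against.** The strongest reply is that the fallback may never be used. Protocol 10.3 is a narrative list, not a field specification, and the eCRF is not among the documents. Criterion 7 cannot be checked without a date, the sponsor confirms key eligibility before randomization (Protocol 7.6), and SAP 3.2.4 expects a date of most recent progression. This stands against one tempting inference, that the comparison is biased as planned: no document shows a single missing date. It does not rescue the rule. The SAP provides for patients without a date, never says that the eligibility or disease-history date may supply it, and then codes a known event as absent.

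The second reply concerns size. A stop date equal to the progression date describes patients taken off therapy for progression, whose date is the most likely to be on file. This stands: with dates missing at random, 1/(1-f) is the largest factor as long as the stop date does not fall after progression.

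A reader might also infer that the whole comparison understates selinexor. The documents do not support that. Prior progression comes from history and study progression from central review, entry selects patients who progressed on the prior line, and study TTP is itself censored. Only the contribution of this rule has a sign.

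Finally, a reader might infer that one-dose patients all but guarantee a TTNT result favouring study treatment. Step 5 shows that this does not follow: the prior clock need not be short, and shares of 49% and 64% are far from certain wins.

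**Conclusion.** The point holds conditionally. SAP 4.2.2.1 treats as event-free, at the stop date, patients whose progression was a condition of entry. To the extent that dates are missing, the rule can shift the patient-stratified HR against selinexor, by up to 1.05, 1.11 or 1.25 at an assumed 5%, 10% or 20% undated, by less if the drug stopped before progression, and by nothing if every date is on file. These figures assume missingness at random, and the documents give no undated share. The argument also takes the current criteria 5 and 7 as those applied at entry; earlier protocol versions are not available.

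The consequences are limited. SAP 4.2.1 and Protocol 7.5.2.1 name only OS as key secondary, although the study flow chart still lists TTP there. SAP 4.2 advises caution with nominal secondary p-values, and the modelled comparison lies within the selinexor arm. The primary PFS test and the OS hierarchy are unaffected. The rule is still worth correcting, because the repair is one sentence and uses a date that the plan already presupposes.

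**What to change.** In SAP 4.2.2.1, replace the censoring sentence:

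- The prior TTP event is the first documented progression after the start of the last prior systemic therapy, taken from the eligibility or disease-history record when the therapy record lacks it. The most recent progression in SAP 3.2.4 should not be substituted unchecked: a patient who progressed, was observed and progressed again would get too long a prior TTP.
- If that date is partial or missing, a patient outside the one-dose exception stays an event known to lie between the start of that therapy and randomization. Place it at the stop date if therapy stopped for progression; otherwise impute between stop date and randomization, with both ends as a sensitivity analysis.
- Report how many patients are affected.

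For one-dose patients, report the number and repeat the TTP and TTNT comparisons without them. Do not redefine the last prior therapy for TTNT while its end point stays at the start of study treatment: the one-dose drug was itself the next treatment, so prior TTNT would be overstated.

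Add the progression date to Protocol 10.3, and reconcile criterion 5 with the exception in criterion 7. Enrollment has closed (SAP 1.1), so this alters no patient's entry.

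The cost is SAP wording, a small amount of extra analysis, and reliance on imputation in the undated cases. It needs no new patients or procedures.
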